E.1. MANAGEMENT OF SPECIFIC ADVERSE EVENTS

The Guidelines for Dose Modification, (protocol section C.5.2), apply to all of the scenarios listed in this section.

E.1.1. Serious Infections

All subjects will be monitored for signs or symptoms of a serious or local infection at each visit. All subjects who develop a serious infection while on study will be referred for immediate medical care to a qualified healthcare professional. Participants who develop any of the following infectious events will be required to discontinue study treatment:

- Tuberculosis, pulmonary or extrapulmonary
- Non-tuberculous mycobacterial infection, disseminated or extrapulmonary
- *Pneumocystis jirovecii* pneumonia
- Coccidioidomycosis, disseminated or extrapulmonary
- Cryptococcosis, extrapulmonary
- Cryptosporidiosis or isosporiasis, chronic intestinal (greater than 1 month's duration)
- Cytomegalovirus disease (other than liver, spleen, or lymph nodes) and including retinitis with loss of vision
- Histoplasmosis, disseminated or extrapulmonary
- Kaposi's sarcoma
- Lymphoma, Burkitt's or immunoblastic, regardless of anatomical location
- Lymphoma, primary of brain
- Progressive multifocal leukoencephalopathy
- Toxoplasmosis of brain
- Herpes zoster reactivation involving more than one dermatome or visceral involvement including but not limited to viral pneumonia, encephalitis and hepatitis.
- Any serious infection that is considered life-threatening or requires inpatient treatment. Participants who experience other serious infections not listed above that do not require inpatient treatment and are not considered life-threatening will have study treatment temporarily stopped until the infection is controlled. These subjects may restart study drug once the infection is controlled.

Other infections, including local infections, will also require referral to qualified medical treatment. The study principal investigator, in consultation with the SMC if necessary, will determine if an infection not listed above warrants permanent treatment discontinuation.

E.1.2. Acute Hypersensitivity Reactions

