 - Lymphoma, primary of brain
 - Progressive multifocal leukoencephalopathy
 - Toxoplasmosis of brain
- Occurrence of herpes zoster reactivation involving more than two dermatomes or visceral involvement including but not limited to viral pneumonia, encephalitis and hepatitis.
- Occurrence of a serious infection that is considered life-threatening or requires inpatient treatment.
- Occurrence of an incident cancer other than a localized basal cell carcinoma of the skin that requires local excision only.
- Requirement for prohibited concomitant medications (see exclusion criteria and section C.6).
- Pregnancy or breastfeeding.
- Deep vein thrombosis or pulmonary embolism.
- Myocardial infarction or other acute coronary syndrome.
- Development of a grade ≥ 3 hypersensitivity reaction, OR a grade 2 hypersensitivity reaction that includes manifestations of angioedema, or suspected or confirmed capillary leak syndrome.
- Development of an ANC < 500 cells/mm³.
- Development of a platelet count $< 50,000$ /mm³.
- Elevation of AST or ALT to > 5 x ULN.
- Serum TSH elevation to ≥ 3.99 mIU/L, abnormal serum T4 or T3 levels, abnormal levels of anti-Tpo antibodies, or symptomatic hypo- or hyperthyroidism.
- Completion of treatment as defined in the protocol.
- Request by participant or his/her healthcare providers to terminate treatment.
- Reasons believed to be clinically significant by the investigators, even if not addressed in the adverse event management section of the protocol.

F.2. PREMATURE STUDY DISCONTINUATION

- Failure by the participant to attend 3 consecutive visits.
- Request by participant or his/her healthcare providers to terminate participation in the study.
- Participant judged by the investigator to be at significant risk of failing to comply with the provisions of the protocol as to cause harm to self or seriously interfere with the validity of the study results.
- At the discretion of the institutional review board (IRB), Office for Human Research Protections (OHRP), FDA, NIAID or investigator.

F.3. TEMPORARY TREATMENT DISCONTINUATION

- Criteria for withholding dose met (refer to section C.5.2 and to Manual of Operations).

G. SAFETY MONITORING

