Adverse events are graded according the Division of AIDS Table for Grading the Severity of Adult and Pediatric Adverse Events, Version 1.0, December 2004 (Clarification, August 2009), which can be found on the DAIDS RSC Web Site: <http://rsc.tech-res.com/safetyandpharmacovigilance/>

H.3.1.2. Adverse Reaction

An *adverse reaction* is defined as any adverse event caused by the use of a drug. Adverse reactions are a subset of all suspected adverse reactions for which there is reason to conclude that the drug caused the event.

H.3.1.3. Suspected

A *suspected* adverse reaction is defined as any adverse event for which there is a reasonable possibility that the drug caused the adverse event. For the purposes of IND safety reporting, “reasonable possibility” indicates that there is evidence to suggest a causal relationship between the drug and the adverse event. A suspected adverse reaction implies a lesser degree of certainty about causality than an adverse reaction.

H.3.1.4. Unexpected

An adverse event or suspected adverse reaction is considered *unexpected* if it is not listed in the package insert, or is not listed with the same characteristics or severity observed in the trial, or is not consistent with the risk information described elsewhere in the current protocol.

Some adverse events are listed in the package insert as occurring with the same class of drugs, or as anticipated from the pharmacological properties of the drug, even though they have not been observed with the drug under investigation. Such events would be considered *unexpected* until they have been observed with the drug under investigation.

H.3.1.5. Serious

An adverse event or suspected adverse reaction is considered *serious* if, in the view of either the investigators or sponsor, it results in any of the following outcomes:

- Death
- Life-threatening adverse event
- Inpatient hospitalization or prolongation of existing hospitalization
- A persistent or significant incapacity or substantial disruption of the ability to conduct normal life function
- Congenital anomaly/birth defect

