In ESPRIT, there was an excess of grade 4 clinical events in the rIL-2 recipients; the same excess was not seen in SILCAAT. Abrams and colleagues (42) have suggested this is via an impact on procoagulant pathways. In ESPRIT, patients with the highest CD4+ T-cell counts in the rIL-2 arm had the greatest relative risk of clinical events, including death. Perhaps, therefore, receipt of rIL-2 primes the patient for a proinflammatory state subsequently associated with more clinical events, and this is amplified in patients with the greatest CD4+ T-cell response to rIL-2, i.e. the ESPRIT cohort, which had higher baseline CD4+ T-cell counts than in SILCAAT. However, it is still important to remember that while rIL-2 receipt in ESPRIT was associated with more embolic

events, overall there was no excess of opportunistic diseases, death or cardiovascular disease and non-AIDS cancers compared with the ART-only arm.

I.6.1.1. Risk Mitigation Strategy for Serious Infections

Although there was no increased risk of infections in the two large phase III clinical trials of IL-2 administration (SILCAAT and ESPRIT), to mitigate the risk of serious infections, individuals with any of the following conditions will be excluded from enrolling in this study:

- A screening CD4 T-cell count <350 cells/mm³
- An absolute neutrophil count <1500 cells/mm³
- An active local or systemic infection
- Use of immunosuppressive or immune modulating therapy
- Use of any investigational agent
- Actively co-infected with HBV or HCV

If a serious infection develops, study drug will be held until the infection is adequately controlled. Study drug administration will be interrupted if the ANC is <1,000 cells/mm³.

I.6.1.2. Risk Mitigation Strategy for Hypersensitivity Reactions

To mitigate the risk of hypersensitivity reactions including anaphylaxis:

- Patients with a known allergy/sensitivity or any hypersensitivity to components of the study drug or its formulation will be excluded.
- The first dose of study agent will be administered in the Special Immunology Unit that has treated more than 50 patients with IL-2 on SILCAAT and ACTG 328 trials. Subjects will be monitored for a minimum of 30 minutes following the first dose of study drug by personnel with life support training and access to adequate life support equipment and resuscitation medication.
- A severe allergic reaction related to study treatment will be grounds for study treatment discontinuation.

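### Section I.6.1.1 holds study drug for any serious infection until it is controlled, while E.1.1 and F.1 require discontinuation for inpatient, life-threatening and listed opportunistic infections

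*Combined protocol and SAP*

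**What the plan says.** Three sections of the combined protocol and SAP deal with study drug after a serious infection.

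- **I.6.1.1 (Risk Mitigation Strategy for Serious Infections):** "If a serious infection develops, study drug will be held until the infection is adequately controlled". The sentence has no exception for severity, place of treatment or type of infection.
- **E.1.1 (Serious Infections)** has two tiers. The first opens with "Participants who develop any of the following infectious events will be required to discontinue study treatment". Its list names specific opportunistic conditions and ends with "Any serious infection that is considered life-threatening or requires inpatient treatment". The second tier covers "Participants who experience other serious infections not listed above that do not require inpatient treatment and are not considered life-threatening"; these participants "will have study treatment temporarily stopped until the infection is controlled" and may then restart. A closing paragraph on other infections says that the principal investigator, consulting the Safety Monitoring Committee (SMC) if needed, "will determine if an infection not listed above warrants permanent treatment discontinuation".
- **F.1 (Permanent Treatment Discontinuation)** lists the same opportunistic conditions and, separately, "Occurrence of a serious infection that is considered life-threatening or requires inpatient treatment".

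H.3.1.5 defines a serious adverse event for reporting purposes. One of its qualifying outcomes is "Inpatient hospitalization or prolongation of existing hospitalization".

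**The concern.** A participant admitted to hospital with an infection falls under all three sections. F.1 ends treatment. I.6.1.1 speaks only of a hold that lasts until the infection is under control. The answer to whether later cycles may be given can therefore depend on which section is consulted.

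What is at stake is mainly consistent safety conduct. Site staff, the IRB and the SMC should all find the same rule.

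There is a smaller consequence for the analysis. Under C.2.1 the on-treatment analysis includes only participants who received all eight cycles, and a further model includes the number of cycles received. One stop-or-restart decision can move a participant into or out of the on-treatment set. With 20 enrolled, that is 1/20 = 5% of the cohort. The intent-to-treat set, which needs only one dose, does not change.

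**Working it through.** No figure is involved, so the check is a comparison of text. The table sets the three sections against each category of serious infection.

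| Category of serious infection | I.6.1.1 | E.1.1 | F.1 | Consistent? |
|---|---|---|---|---|
| Unlisted, no inpatient care, no threat to life | Hold until controlled | Temporary stop until controlled; may restart | Not named | Yes |
| Inpatient care or threat to life | Hold until controlled | Discontinue | Permanent discontinuation | No |
| Listed opportunistic infection, where it counts as serious | Hold until controlled | Discontinue | Permanent discontinuation | No |

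**Step 1: does discontinuation in E.1.1 mean permanent?** The lead-in to the list does not use that word. Two features of the section point that way: the contrast with the temporary stop in the second tier, and the closing paragraph, which leaves permanent discontinuation to be decided only for infections that are not listed. F.1 settles it by its heading.

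**Step 2: does I.6.1.1 reach the second and third rows?** E.1.1 uses the term serious infection for both of its tiers, so the unqualified term in I.6.1.1 covers both. To confine I.6.1.1 to the first row, a reader has to supply a qualifier that E.1.1 contains and I.6.1.1 lacks. H.3.1.5 fits this, since it counts hospitalisation and threat to life as making an event serious. It does not settle the matter, because it also admits important medical events that involve neither.

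**Step 3: is I.6 only a summary that leaves stopping rules to other sections?** Not consistently.
- I.6.1.4.4 (thyroid), I.6.1.4.5 (renal) and I.6.1.6 (recurrent or multidermatomal zoster) state permanent stops.
- I.6.1.3 gives no stop for deep vein thrombosis, and I.6.1.4.3 omits the stop above 5 times the upper limit of normal. E.1 and F.1 contain both.
- I.7.2 refers the reader back to I.6 for the details of risk minimisation in each category.

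I.6 is therefore not a complete stopping list, but it is presented as more than background.

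**Step 4: does any text say which section governs?** I found no precedence rule between sections, and I.6.1.1 has no cross-reference to E.1.1 or F.1.

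**The case against.** The strongest reply is that I.6.1.1 simply restates E.1.1's second tier, for which the two rules match, and that its silence on permanent stops does not contradict F.1. Holding drug during an infection and then discontinuing it permanently would satisfy both sections. E.1.1 and F.1 are the operative rules, and they agree on inpatient and life-threatening infections. Section G also has the investigators review every adverse event of grade 2 or above in real time and decide whether it meets discontinuation criteria. A hospitalised infection would therefore normally be checked against F.1 before another cycle.

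Much of this stands, and it limits the severity. It does not remove the inconsistency. The hold in I.6.1.1 ends when the infection is controlled, and the sentence has no wording that limits it to the milder tier.

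Two stronger readings are tempting, and the documents support neither.
- **That I.6.1.1 orders a restart after a hospitalised infection.** It does not. Resumption is implied by a hold with an end point. It is not stated, unlike in E.1.1's second tier or the neutropenia plan in I.6.1.4.1.
- **That a serious infection is by definition inpatient or life-threatening, so that I.6.1.1 conflicts with F.1 in every case it covers.** H.3.1.5 includes events that are neither, and E.1.1 describes serious infections that are neither. For those, I.6.1.1 and E.1.1 agree.

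**Conclusion.** The inconsistency is real and limited. For serious infections that need inpatient care or threaten life, and for listed opportunistic infections that are serious, I.6.1.1 read alone could be taken to allow a restart that F.1 rules out. For the remaining serious infections the sections agree.

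Severity is low to moderate. All three sections stop drug at onset and can differ only at a later restart decision. I.6.1.1 itself notes no increased infection risk in the two large phase III trials. The documents do not give the expected frequency of such infections here, so the number of participants affected among the 20 cannot be estimated. No effect on the primary endpoint, the sample size or the intent-to-treat set has been shown.

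The conclusion assumes that discontinuation in E.1.1 means permanent discontinuation, as F.1 states. It also assumes that the Manual of Operations, which is not among the documents reviewed, does not already resolve the point.

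**What to change.** Reconcile I.6.1.1 with E.1.1 and F.1, by rewording or by explicit cross-reference, so that one rule applies to each of three categories: listed opportunistic infections; other serious infections that are inpatient or life-threatening; and the remaining serious infections. State for each whether treatment may restart. Which rule is clinically right is for the investigators and the sponsor to decide; this review takes no position on it.

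The cost is about a sentence of protocol wording, handled through the amendment process, plus a check that the Manual of Operations matches. The design, visit schedule and analysis plan need not change.

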The progression of thyroid dysfunction during rIL-2 treatment is variable, but it is thought to involve an initial period of thyroid stimulation akin to autoimmune thyroiditis, which is usually undetected, followed by variable degrees of hypothyroidism (50, 55, 57). The mechanisms of these effects on the thyroid are incompletely understood. It has been proposed that IL-2-mediated induction of proinflammatory cytokine production may trigger the initial autoimmune thyroiditis (48, 50, 51). This notion is supported by the finding of increased lymphocyte infiltration of the thyroid, with features suggestive of autoimmune thyroiditis, during rIL-2 treatment (58, 59). In this model, the initial thyroiditis may result from enhancement of class II expression and presentation of autoantigens by thyrocytes due to increased local release of proinflammatory cytokines by thyroid-infiltrating mononuclear cells (48, 51). The clinical course of rIL-2-induced thyroid dysfunction has not been comprehensively described, but at least in some cases, there is spontaneous resolution of the thyroid abnormalities. In a closely monitored study of a single cycle of rIL-2 administered to 20 euthyroid HIV-infected participants, there was a rapid concomitant rise in TSH, T3, T4, and free T4 within the first three days of treatment, with return of all indices to baseline after approximately 14 days (55). The need for thyroid hormone replacement for rIL-2-induced hypothyroidism has been variable and inconsistently reported. In 3 out of 7 participants who developed hypothyroidism in a trial of rIL-2 given with LAK cells for malignant diseases, thyroid function tests returned to normal while these participants were not receiving thyroid replacement, but the authors indicate that they could not ascertain the course of thyroid dysfunction for other participants (49). In a similar study of cancer patients, thyroid function tests returned to the normal range in the absence of thyroid replacement therapy approximately 6 months after treatment among 4 of the 7 participants with rIL-2-induced hypothyroidism. The remaining 3 participants received levothyroxine and also had normal thyroid tests 6 months after rIL-2 treatment, but it is unclear if thyroid replacement had been discontinued by that time (48). In a study including 49 HIV-infected participants randomized to either low (1.5 MIU

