SC BID) or high (7.5 MIU SC BID) dose rIL-2, 2 of the 5 participants who developed hypothyroidism did not receive thyroid replacement therapy, but the duration of thyroid replacement and the follow-up results of thyroid function tests were not reported (33).

Risk factors for thyroid dysfunction during rIL-2 treatment include female sex, pre-existing thyroid dysfunction, large cumulative doses of rIL-2, and importantly, the presence of anti-thyroid antibodies (49, 50, 57). The association of IL-2 thyroid dysfunction with the presence of anti-thyroid antibodies has not been accurately quantified, but it has been observed in multiple reported studies (48, 49, 52). In one study including 34 cancer patients, antithyroid antibodies were present in none of the 27 participants who remained euthyroid during treatment, but were present in 5 out of the 7 (71%) participants who developed hypothyroidism (49, 52). Therefore, in this study, participants will be screened for the presence of anti-thyroid antibodies (in addition to routine thyroid function testing) both at study entry and before each rIL-2 cycle. Participants who have abnormal thyroid function tests or elevated levels of antithyroid antibodies at screening will be excluded. Participants who develop abnormal thyroid function tests or antithyroid antibodies at any time during study participation will be required to discontinue study treatment permanently.

Patients may experience mental status changes when taking rIL-2, including irritability, insomnia, confusion, or depression. Mental status changes due solely to rIL-2 are generally reversible when drug administration is discontinued. However, alterations in mental status may continue for several days before recovery begins.

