- Delivery of pre-filled cycle doses of rIL-2 and review of handling, storage, and administration procedures
- CBC and metabolic panel
- Thyroid function tests and anti-Tpo antibodies
- CD4+ and CD8+ T cell count (both absolute and as percent of lymphocytes)
- Plasma HIV RNA level by PCR (using the locally available assay)
- PBMC will be cryopreserved for assays of immune cell phenotype and NK cell phenotype
- Plasma will be cryopreserved for single copy HIV RNA assay
- The participant will be observed as he/she administers the dose of rIL-2 (approximately 5 million units) subcutaneously.

D.2.6. rIL-2 Treatment Cycles 4 and 8, Day 7

Participant returns to clinic for:

- Interval history and complete physical examination.
- Concomitant medication review
- Tolerance and compliance with injection schedule
- CBC and metabolic panel
- CD4+ and CD8+ T cell count (both absolute and as percent of lymphocytes)
- Plasma HIV RNA level by PCR (using locally available assay)
- PBMC will be cryopreserved for assays of immune cell phenotype and NK cell phenotype
- Plasma will be cryopreserved for single copy HIV RNA assay

D.2.7. rIL-2 Treatment Cycles 2 and 3, Day 0

NOTE: Each treatment cycle should begin 7-10 weeks after start of last treatment cycle. These visits will include:

- Interval history and targeted physical examination, including weight.
- Concomitant medication review.
- Delivery of pre-filled cycle doses of rIL-2 and review of handling, storage, and administration procedures

- CBC and metabolic panel
- Thyroid function tests and anti-Tpo antibodies
- CD4+ and CD8+ T cell count (both absolute and as percent of lymphocytes)
- Plasma HIV RNA level by PCR (using the locally available assay)
- IL-2 immunogenicity (cycle 2 only)

D.2.8. rIL-2 Treatment Cycles 5, 6, and 7, Day 0

NOTE: Each treatment cycle should begin 7-10 weeks after start of last treatment cycle. These visits will include:

- Interval history and targeted physical examination, including weight.
- Concomitant medication review.
- Delivery of pre-filled cycle doses of rIL-2 and review of handling, storage, and administration procedures
- CBC and metabolic panel
- Thyroid function tests and anti-Tpo antibodies
- CD4+ and CD8+ T cell count (both absolute and as percent of lymphocytes)
- Plasma HIV RNA level by PCR (using the locally available assay)

D.2.9. rIL-2 Treatment cycles 1-8, Days 2 and 4

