Staff will contact the participant by phone to assess tolerance and compliance with injection schedule

D.2.10. End of Study Visit (or Premature Discontinuation Visit)

NOTE: The end of study visit should take place 8 weeks (+/- 2 weeks) after Day 0 of the last (8th) treatment cycle. In the case of premature discontinuation, the end of study visit should take place at least 6 weeks after day 0 of the last treatment cycle and may take place up to 10 weeks after day 0 of the last treatment cycle.

These visits will include:

- Interval history and targeted physical examination.
- Immunogenicity testing
- CD4+ and CD8+ T cell count (both absolute and as percent of lymphocytes)
- Plasma HIV RNA level by PCR (using the locally available assay)
- IL-2 immunogenicity
- At this visit the participant will undergo a 4 Liter leukapheresis at the Seidman Ambulatory Stem Cell Transplant Unit at University Hospitals using AIDS protocol 328.
- Plasma will be cryopreserved for single copy HIV RNA assay
- Leukapheresis product PBMC will be cryopreserved for:
 - HIV reservoir assay by EDITS
 - HIV reservoir assay by QVOA
 - Total and intact proviral DNA assay (Accelavir)
 - Assays of immune cell phenotype and NK cell phenotype

If leukapheresis cannot be done after premature treatment discontinuation for any reason, a 120 cc. blood draw will be obtained for preparation of PBMC and plasma. Based upon cell yield these samples will be used for:

- Plasma will be cryopreserved for single copy HIV RNA assay
- HIV reservoir assay by EDITS
- HIV reservoir assay by QVOA
- Total and intact proviral DNA assay (Accelavir)
- Assays of immune cell phenotype and NK cell phenotype

D.2.11. Immunogenicity follow-up

Participants who have detectable neutralizing antibodies at the end of study visit will be followed approximately every 90 days for repeat testing until 12 months after the end of study or until a negative result is obtained. During these visits, an interval medical history and targeted physical exam will be conducted. If clinically significant events have occurred, the participant will be referred for appropriate medical care.

D.2.12. Management of off-window visits

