- Previous report of similar AEs associated with rIL2
- Recurrence of the AE after re-challenge or resolution after de-challenge.

The terms used to assess the relationship of an event to rIL2 are:

- Definitely related – The AE is **clearly related** to rIL2
- Probably related – The AE is **likely related** to rIL2
- Possibly related – The AE **may be related** to rIL2

- Probably not related – The AE is **not likely related** to rIL2
- Not related – The AE is **clearly NOT related** to rIL2

When an AE is assessed as “not related” to rIL2, an alternative etiology, diagnosis or explanation for the AE will be provided. If new information becomes available, the relationship to assessment of any AE will be reviewed and updated, as required.

H.3.8. Expedited AE Reporting Period

The protocol-defined EAE Reporting Period for this protocol is the entire study duration for an individual participant (from study enrollment until study completion or discontinuation of the participant from study participation for any reason). After the protocol-defined AE reporting period, unless otherwise noted, only SUSARs as defined in Version 2.0 of the DAIDS EAE Manual will be reported if the study staff become aware of the events on a passive basis (from publicly available information).

H.3.9. Reporting Procedures

All participants will be followed for possible adverse events throughout their involvement in the study, including issues with study conduct. At each study visit, research staff will elicit participant input as to discomforts or adverse experiences. All grade ≥ 2 AEs will be reported to the Principal Investigators on a daily basis. A complete blood count, metabolic panel as defined in D.3.5.1, CD4 T cell count, and plasma HIV-1 RNA level will be performed on most visits. The Principal Investigator will obtain these safety data in “real-time” (i.e., within 1-10 days of a study visit) when laboratory values become available. The Principal Investigators will review these data within that timeframe, assess degree of severity, and assess the relationship to study agent/intervention.

The following adverse events will be reported: adverse events graded 3 and above, and any possibly, probably, or definitely related, unexpected, and serious adverse events. These AEs will be reported to the Safety Monitoring Committee (SMC), and FDA. Reporting to the UHCMC IRB will follow current UHCMC IRB policy (see section H.4.3).

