I.6.1.3. Risk Mitigation Strategy for Thromboembolic Disease

In the ESPRIT trial but not among participants in the SILCAAT trial, there was an increased occurrence of vascular events (but not in cardiac disorders) that were seen among 40 of 466 patients receiving IL-2 plus ART and 14 of 386 receiving ART alone. The most frequent vascular event was deep vein thrombosis seen in 10 IL-2 plus ART recipients and in 2 ART alone recipients. To mitigate risk for vascular events in this trial, persons with a history of venous thrombosis will be excluded from participation and at each visit, signs and symptoms of venous thrombosis will be sought.

I.6.1.4. Risk Mitigation Strategy for Laboratory Abnormalities

I.6.1.4.1. Neutropenia

The risk mitigation plan for neutropenia includes:

- Participants with an ANC <1500 cells/mm³ will not be permitted to enroll in the study;
- ANC will be measured at each clinic visit
- Should the ANC decrease to ≥500 but ≤1,000 cells/mm³, the rIL-2 dose will be interrupted until the ANC is >1,000 cells/mm³ and then rIL-2 will be restarted at 3.5 million units twice daily. If the ANC remains above 1,000 cells/mm³, this dose will be continued until the end of the study.
- Should the ANC decrease ≥500 but ≤1,000 cells/mm³ while on the reduced dose of 3.5 million units twice daily, rIL2 will be discontinued until the ANC reaches 1,000 cells/mm³, and then resumed at a dose of 2 million units twice daily. If the ANC then remains above 1,000 cells/mm³, this dose will be continued until the end of study. If the ANC falls again to ≤1,000 cells/mm³ while on the reduced 2 million unit twice daily dose, rIL2 will be permanently discontinued.
- Should the ANC decrease to <500 cells/mm³, rIL_2 will be discontinued.

I.6.1.4.2. Thrombocytopenia

The risk mitigation plan for thrombocytopenia includes:

- Participants with a platelet count <150,000/mm³ will not be enrolled in the study;
- Platelet counts will be measured at each clinic visit;
- Should the platelet count decrease to ≥50,000 but ≤100,000/mm³ the rIL-2 dose will be interrupted until the platelet count is >100,000/mm³ and then IL-2 will be restarted at 3.5 million units twice daily. If the platelet count remains above 100,000 /mm³, this dose will continue until the end of the study.

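### The end-of-study/discontinuation visit lists no CBC or metabolic panel, contrary to section I.6.1.4, and no thyroid test is scheduled after the final rIL-2 cycle

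*Combined protocol and SAP*

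**What the plan says.** Section I.6.1.4, on mitigating laboratory abnormalities, sets the frequency of the safety labs. For neutrophils, I.6.1.4.1 states "ANC will be measured at each clinic visit". The same frequency is given for platelets (I.6.1.4.2), AST and ALT (I.6.1.4.3) and creatinine (I.6.1.4.5).

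Section H.3.9 is looser. It covers the CBC in the same sentence as "metabolic panel as defined in D.3.5.1, CD4 T cell count, and plasma HIV-1 RNA level will be performed on most visits". The synopsis, under Safety Monitoring, is looser again: labs before each cycle, on Day 7 of some cycles, and when clinically indicated.

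Section D.2.10 defines the last visit. For completers, "The end of study visit should take place 8 weeks (+/- 2 weeks) after Day 0 of the last (8th) treatment cycle". For those who stop early, "the end of study visit should take place at least 6 weeks after day 0 of the last treatment cycle", and at most 10 weeks after it. The list has history and targeted examination, immunogenicity, CD4/CD8 counts, plasma HIV RNA, leukapheresis and stored samples. It has no CBC, metabolic panel, thyroid tests or anti-Tpo.

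On the thyroid, section A.5 promises screening for antibodies and function "both at study entry and before each rIL-2 cycle". It also says: "Risk factors for thyroid dysfunction during rIL-2 treatment include female sex, pre-existing thyroid dysfunction, large cumulative doses of rIL-2", and describes an initial stimulation phase "which is usually undetected, followed by variable degrees of hypothyroidism".

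**The concern.** The protocol gives conflicting instructions for one visit. Staff working from D.2.10 would draw no blood count or chemistry; staff working from I.6.1.4 would draw both.

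The visit matters because it is the last one for every participant, including those who stop early. Someone who stops dosing may have had doses since their last CBC, liver enzymes and creatinine. If they go directly to D.2.10, they can leave the study with no scheduled check of those values. Participants withdrawn for a low neutrophil or platelet count or for raised transaminases (section F.1) also have no listed recheck at this visit, although E.2.2 asks that Grade 3 and 4 events be followed to Grade 2 or below.

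The thyroid point is different in kind: it is a gap in coverage, not a contradiction. Each of cycles 1 to 7 is followed by a thyroid test at the next Day 0. Cycle 8 is followed by none, although cumulative exposure is then highest and the protocol itself expects early dysfunction to go unnoticed. An asymptomatic abnormality arising after the last cycle would not reach the participant, or the safety reports described in section G, through any scheduled test.

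**Working it through.** No sample size, power or error-rate figure is involved. The check compares the visit lists in D.2.1 to D.2.10 with the frequency statements and works out the intervals.

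**Scheduled clinic visits for a full course**

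| Visit | Section | Number | CBC and panel | Thyroid and anti-Tpo |
|---|---|---|---|---|
| Screening | D.2.1 | 1 | yes | yes |
| Baseline leukapheresis | D.2.2 | 1 | yes | yes |
| Day 0, cycles 1–8 | D.2.3, D.2.5, D.2.7, D.2.8 | 8 | yes | yes |
| Day 7, cycles 1, 4, 8 | D.2.4, D.2.6 | 3 | yes | no |
| End of study or discontinuation | D.2.10 | 1 | **no** | **no** |

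- Total: 1 + 1 + 8 + 3 + 1 = 14.
- CBC and panel: 1 + 1 + 8 + 3 = 13 of 14. D.2.10 is the only omission.
- Thyroid and anti-Tpo: 1 + 1 + 8 = 10 of 14, the last at cycle 8 Day 0.

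Telephone contacts on Days 2 and 4 (D.2.9) and the conditional immunogenicity visits (D.2.11) are not counted.

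**Intervals for completers.** The final visit is 8 ± 2 weeks after cycle 8 Day 0, that is 6 to 10 weeks.

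- Last listed CBC and panel (D.2.6, "rIL-2 Treatment Cycles 4 and 8, Day 7"): 6 − 1 = 5 to 10 − 1 = 9 weeks before the final visit.
- Last listed thyroid test (cycle 8 Day 0): 6 to 10 weeks before the final visit, and before that cycle's doses.

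**Intervals for early stoppers who go directly to D.2.10.** That visit is 6 to 10 weeks after Day 0 of the last cycle.

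- Last cycle 1 or 4: a Day 7 CBC and panel exists, so the interval is again 5 to 9 weeks.
- Last cycle 2, 3, 5, 6 or 7: there is no Day 7 visit. The last listed CBC, panel and thyroid tests were drawn at that cycle's Day 0, 6 to 10 weeks earlier, and no listed safety lab follows the doses.

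**Comparison within the protocol.** The baseline leukapheresis visit (D.2.2) lists a CBC, panel and thyroid tests. D.2.10 repeats the same 4-litre procedure without them and names immunogenicity testing twice, which suggests an omission in drafting.

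**Scale of the thyroid risk.** Section A.5 gives a frequency of 2.5% to 11.7% in small studies of subcutaneous rIL-2 in HIV, and an informal estimate of 10% to 15% for the two large trials. For 20 participants that is 20 × 0.025 = 0.5 to 20 × 0.15 = 3 cases over the whole study. The documents do not say what share would first appear after cycle 8.

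**The case against.** The strongest reply is that the conflict is mainly one of wording. The synopsis and H.3.9 both describe less than universal testing, D.2 matches them, and I.6.1.4 is the outlier. Its statements sit beside rules for holding, reducing and stopping rIL-2, and no dosing decision remains at the last visit. Editing I.6.1.4 would also remove the inconsistency. That is true, but it would leave early stoppers without a scheduled check after their last doses.

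Section C.1 says efforts will be made to keep people on the schedule after rIL-2 is stopped, and the remaining Day 0 visits include the labs. A participant stopped on a pre-cycle Day 0 result already has labs after the last cycle received. Both points stand: the early-stopper gap is confined to those who go straight to D.2.10 after a cycle without a Day 7 visit and without such a result. How many would do so is unknown.

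The thyroid schedule delivers what A.5 promises. A.5 also reports that after a single cycle in 20 HIV-infected participants the indices returned to baseline in about 14 days, and that some cases resolve on their own. It adds that the course varies, so this limits the worry without removing it. A test at 6 to 10 weeks would fall well after that transient.

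Most toxicities are said to resolve within 5 days of a cycle (A.5), completers have Day 7 labs after cycle 8, and clinically indicated tests remain available. The schedule chart is in the Manual of Operations, which is not part of these documents and may list the tests. If it does, D.2.10 still disagrees with it. These points bound the consequence; they do not reconcile D.2.10 with I.6.1.4.

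**Conclusion.** The concern holds. D.2.10 contradicts I.6.1.4 for the CBC and metabolic panel, and the absence of a thyroid test after the final cycle is a separate gap in coverage.

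The consequence is moderate. At most 20 participants are exposed to the gap at the final visit; those with no listed safety labs at all after their last cycle are an unknown subset of early stoppers. The conclusion concerns scheduled tests as written in the protocol. It does not assume that clinically indicated tests would be withheld, and it makes no claim about the Manual of Operations chart. The primary endpoint, its analysis and the dosing rules are untouched. The change should be made because the visit closes safety follow-up and the remedy is small.

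**What to change.** Add to D.2.10, for completers and early stoppers alike: CBC, metabolic panel, TSH, T3, T4 and anti-Tpo antibodies.

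Revise H.3.9 so that the CBC and metabolic panel are stated for each clinic visit, in line with I.6.1.4. Leave the looser frequency for plasma HIV RNA, since the baseline leukapheresis visit (D.2.2) lists only stored plasma and no real-time result. Bring the synopsis wording into line and confirm that the schedule chart in the Manual of Operations agrees.

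The cost is one routine lab set per participant, so at most 20, at a visit where blood is already drawn. No visit is added. An abnormal result would need referral after study participation ends, and the plan should say who makes it.
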